8.2.2. Clinically Notable Adverse Events

Specific groupings of clinically notable AEs will be considered and the number of participants with at least 1 event within each grouping will be reported. Such groups consist of AEs for which there is a specific clinical interest in connection with pemigatinib or AEs that are similar in nature (although not identical). The groups are defined as per [Table 4](#). All clinically notable AEs are defined through reviewing PT according to the current MedDRA v21.1.

Table 4: Clinically Notable Adverse Events Groupings

Categories	Preferred Terms
Serous retinal detachment	Serous retinal detachment, detachment of macular retinal pigment epithelium, detachment of retinal pigment epithelium, retinal detachment, subretinal fluid, chorioretinopathy, retinal pigment epitheliopathy, chorioretinal disorder, retinopathy, maculopathy, retinal disorder, retinal thickening, chorioretinal folds, chorioretinal scar
Nail toxicity	Nail toxicity, nail bed tenderness, nail bed disorder, nail bed bleeding, nail disorder, nail discolouration, nail discomfort, nail dystrophy, nail hypertrophy, nail ridging, nail infection, onychalgia, onychoclasia, onycholysis, onychomadesis, onychomycosis, paronychia, fungal paronychia
Hyperphosphatemia	Hyperphosphataemia, blood phosphorus increased
Hypophosphatemia	Hypophosphataemia, blood phosphorus decreased
Dry eye	Dry eye, meibomian gland dysfunction, lacrimation increased, keratitis, punctate keratitis, pinguecula, pterygium
eyelash changes	Eyelash changes, growth of eyelashes, trichiasis, trichomegaly
vision blurred	vision blurred, visual impairment, visual acuity reduced
vitreous detachment	Vitreous detachment, vitreous floaters

8.2.3. Adverse Event Summaries

An overall summary of AEs by cohorts will include:

- Number (%) of participants reporting any TEAEs
- Number (%) of participants reporting any serious TEAEs
- Number (%) of participants reporting any Grade 3 or higher TEAEs
- Number (%) of participants reporting any TEAEs related to pemigatinib
- Number (%) of participants who temporarily interrupted pemigatinib because of TEAEs
- Number (%) of participants who permanently discontinued pemigatinib because of TEAEs
- Number (%) of participants with pemigatinib dose reductions because of TEAEs
- Number (%) of participants who had a fatal TEAE

The following summaries will be produced by MedDRA term:

- Summary of TEAEs by MedDRA SOC and PT
- Summary of TEAEs by MedDRA PT in decreasing order of frequency
- Summary of TEAEs by MedDRA SOC, PT, and maximum severity
- Summary of TEAEs by MedDRA SOC, PT, and CTCAE Grade Category
- Summary of Grade 3 or higher TEAEs by MedDRA SOC and PT
- Summary of Grade 3 or higher TEAEs by MedDRA PT in decreasing order of frequency
- Summary of serious TEAEs by MedDRA SOC and PT
- Summary of serious TEAEs by MedDRA PT in decreasing order of frequency
- Summary of pemigatinib treatment-related AEs by MedDRA SOC and PT
- Summary of pemigatinib treatment-related TEAEs by MedDRA PT in decreasing order of frequency
- Summary of Grade 3 or higher pemigatinib treatment-related TEAEs by MedDRA SOC and PT
- Summary of pemigatinib treatment-related serious TEAEs by MedDRA SOC and PT
- Summary of TEAEs with a fatal outcome by MedDRA SOC and PT
- Summary of TEAEs leading to pemigatinib dose reduction by MedDRA SOC and PT
- Summary of TEAEs leading to pemigatinib dose interruption by MedDRA SOC and PT
- Summary of TEAEs leading to discontinuation of pemigatinib by MedDRA SOC and PT

- Summary of sponsor-defined clinically notable TEAEs by category and PT
- Summary of Grade 3 or higher sponsor-defined clinically notable TEAEs by category and PT
- Summary of serious sponsor-defined clinically notable TEAEs by category and PT
- Summary of sponsor-defined clinically notable TEAEs leading to pemigatinib dose reduction by category and PT
- Summary of sponsor-defined clinically notable TEAEs leading to pemigatinib dose interruption by category and PT
- Summary of sponsor-defined clinically notable TEAEs leading to discontinuation of pemigatinib by category and PT

8.3. Clinical Laboratory Tests

8.3.1. Laboratory Value Definitions

Laboratory values and change from baseline values will be summarized descriptively by visit for numeric laboratory parameters. Baseline will be determined according to Section 4.1.3. If there are multiple values that meet the criteria for baseline, additional rules may be provided after consultation with the medical monitor to delineate which value will be defined as baseline.

Laboratory test values outside the normal range will be assessed for severity based on the numerical component of CTCAE v5.0.

8.3.2. Laboratory Value Summaries

All test results and associated normal ranges from central laboratories will be reported in SI units. All tests with numeric values will have a unique unit. Any laboratory test results and associated normal ranges from local laboratories will be converted to SI units.

For numeric laboratory values, baseline value, postbaseline value, change from baseline, and percentage change from baseline will be summarized descriptively by visit. The number and percentage of participants with the laboratory values being low, normal, and high will be summarized by visit. In addition, mean change from baseline will be plotted over time for selected laboratory parameters, including phosphate.

Severity grades will be assigned to laboratory test values based on the numerical component of CTCAE v5.0. Shift tables will be presented showing change in CTCAE grade from baseline to worst grade postbaseline. Separate summaries for abnormally high and abnormally low laboratory values will be provided when the laboratory parameter has both high and low grading criteria. The denominator for the percentage calculation will be the number of participants in the baseline category. The number of participants who experienced worsening of laboratory abnormalities will be summarized by maximum severity.

8.3.3. Potential Hy's Law Events

The participants with elevated ALT or AST $> 3 \times$ upper limit of normal range and alkaline phosphatase $< 2 \times$ upper limit of normal range accompanied by total bilirubin $> 2 \times$ upper limit of normal range at the same visit will be listed by cohort.

8.4. Vital Signs

Values at each scheduled visit, change, and percentage change from baseline for vital signs, including weight, systolic blood pressure, diastolic blood pressure, pulse, temperature, and respiratory rate will be summarized descriptively.

Normal ranges for vital sign values are defined in [Table 5](#). The abnormal values for participants exhibiting vital sign abnormalities will be listed along with their cohort. Alert vital signs are defined as an absolute value outside the defined normal range and percentage change greater than 25%. Note that the definition of alert vital signs does not apply for body temperature and weight. The abnormal values for participants exhibiting alert vital sign abnormalities will be listed.

Table 5: Criteria for Clinically Notable Vital Sign Abnormalities

Parameter	High Threshold	Low Threshold
Systolic blood pressure	> 155 mmHg	< 85 mmHg
Diastolic blood pressure	> 100 mmHg	< 40 mmHg
Pulse	> 100 bpm	< 45 bpm
Temperature	$> 38^{\circ}\text{C}$	$< 35.5^{\circ}\text{C}$
Respiratory rate	> 24 breaths/min	< 8 breaths/min

8.5. Electrocardiograms

Twelve-lead ECGs including the heart rates and PR, QT, QRS, and QTc intervals will be obtained for each participant during the study. Values at each scheduled visit, change, and percentage change from baseline will be summarized for each ECG parameter. Baseline will be determined as the average of all nonmissing values before the first administration of pemigatinib.

Normal ranges for ECG values are defined in [Table 6](#). ECG values will also be considered abnormal if the absolute percentage change from baseline is more than 25% (QRS 30%). Participant exhibiting ECG abnormalities will be listed with study visit and assigned cohort. Abnormal values for participant with alert ECG values, defined as both the absolute value and the percentage change from baseline being outside normal ranges, will be identified and listed. Outliers of QT, and QTc values, defined as absolute values > 450 ms, > 500 ms, or change from baseline > 30 ms, will be summarized.

Table 6: Criteria for Clinically Notable Electrocardiogram Abnormalities

Parameter	High Threshold	Low Threshold
HR	> 100 bpm	< 45 bpm
PR	> 220 ms	< 75 ms
QT	> 500 ms	< 300 ms
QRS	> 120 ms	< 50 ms
QTc	> 460 ms	< 295 ms

9. INTERIM ANALYSIS

For Cohort A, futility analysis will be performed when approximately 25 participants are enrolled into the cohort and have at least 2 objective tumor response assessments per independent centralized radiological review or are discontinued from the study. Cohort A can be stopped for futility if ≤ 4 responders are observed, for which there is $< 10\%$ probability of claiming ORR $> 15\%$ at final analysis. This rule is just a guidance and nonbinding.

For Cohort B, futility analysis will be performed when approximately 35 participants are enrolled into the cohort and have at least 2 objective tumor response assessments per independent centralized radiological review or are discontinued from the study. Cohort B can be stopped for futility if ≤ 6 responders are observed, for which there is approximately 14% probability of claiming ORR $> 15\%$ at final analysis. This rule is just a guidance and nonbinding.

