## **10. STATISTICS**

### **10.1. Sample Size Determination**

For Cohort A, approximately 60 participants are planned. Assuming the true ORR is 35% for the intervention in this group, 60 participants are needed to ensure that there is at least 90% power to test the null hypothesis of  $ORR \leq 15\%$ . This calculation assumes 1-sided test at the overall 0.025 level of significance.

For Cohort B, approximately 90 participants are planned. Assuming the true ORR is 30% for the intervention in this group, 90 participants are needed to endure that there is at least 90% power to test the null hypothesis of  $ORR \leq 15\%$ . This calculation assumes 1-sided test at the overall 0.025 level of significance.

For Cohort C, approximately 20 participants will be enrolled, which will provide at least 80% chance of observing at least 4 responders in this cohort if the underlying ORR is 30%.

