## **10.5. Interim Analysis**

For Cohort A, futility analysis will be performed when approximately 25 participants are enrolled into the cohort and have at least 2 objective tumor response assessments per independent centralized radiological review or are discontinued from the study or are discontinued from treatment without post-treatment tumor assessments. Cohort A can be stopped for futility if  $\leq 4$  responders are observed in RECIST/RANO evaluable population, for which there is  $< 10\%$  probability of claiming ORR  $> 15\%$  at final analysis. This rule is just a guidance and nonbinding.

For Cohort B, futility analysis will be performed when approximately 35 participants are enrolled into the cohort and have at least 2 objective tumor response assessments per independent centralized radiological review or are discontinued from the study or are discontinued from treatment without post-treatment tumor assessments. Cohort B can be stopped for futility if  $\leq 6$  responders are observed in RECIST/RANO evaluable population, for which there is approximately 14% probability of claiming ORR  $> 15\%$  at final analysis. This rule is just a guidance and nonbinding.

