3.2. Control of Type I Error

For the primary endpoint, the overall 1-sided Type I error is 0.025. The primary endpoint in Cohort A and Cohort B will be tested sequentially at 1-sided 0.025. If ORR in Cohort A is significant, then ORR in Cohort B will be tested.

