3.3. Sample Size Considerations

For Cohort A, approximately 60 participants are planned. Assuming the true ORR is 35% for the intervention in this group, 60 participants are needed to ensure that there is at least 90% power to reject the null hypothesis of $ORR \leq 15\%$. This calculation assumes 1-sided test at the overall 0.025 level of significance.

For Cohort B, approximately 90 participants are planned. Assuming the true ORR is 30% for the intervention in this group, 90 participants are needed to ensure that there is at least 90% power to reject the null hypothesis of $ORR \leq 15\%$. This calculation assumes 1-sided test at the overall 0.025 level of significance.

For Cohort C, approximately 20 participants will be enrolled, which will provide at least 80% chance of observing at least 4 responders in this cohort if the underlying ORR is 30%.

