7.1. Efficacy Hypotheses

Objective Response Rate (Primary Endpoint): Administration of pemigatinib to participants in Cohort A and B improves ORR from 15%. Assume ORR_A and ORR_B are the ORRs for cohort A and B respectively.

The hypotheses for Cohort A are as follows:

- H_0 (null hypothesis): $ORR_A \leq 15\%$
- H_A (alternative hypothesis): $ORR_A > 15\%$

The hypotheses for cohort B are as follows:

- H_0 (null hypothesis): $ORR_B \leq 15\%$
- H_A (alternative hypothesis): $ORR_B > 15\%$

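### The Cohort B power of at least 90% leaves out the planned futility look; with the 6-of-35 guidance followed, power at an ORR of 30% is about 89%

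*SAP*

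**What the plan says.** SAP 3.3 plans about 90 participants in Cohort B, takes the true ORR to be 30%, and states that "90 participants are needed to ensure that there is at least 90% power to" reject the null hypothesis of an ORR of 15% or less. Protocol 10.1 makes the same claim: "90 participants are needed to endure that there is at least 90% power to test the null hypothesis". Both use a 1-sided 0.025 level, and SAP 7.2.1 specifies the exact binomial test. Neither sample size section mentions an interim look.

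The look is described in SAP 9 and Protocol 10.5. When about 35 Cohort B participants are evaluable, the cohort can be stopped if 6 or fewer "responders are observed, for which there is approximately 14% probability of claiming ORR" above 15% at the final analysis. The Protocol gives the same figure ("for which there is approximately 14% probability of claiming"). For Cohort A the look is at about 25 participants, the limit is 4 or fewer responders, and the stated probability is below 10%. Both rules are described as guidance and nonbinding. Neither document says how the two probabilities were calculated or what power remains if the guidance is followed.

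**The concern.** A futility look costs power. Some cohorts that truly have the planned response rate start slowly, meet the limit and are stopped, although a share of them would have succeeded at full size. Being nonbinding does not remove this cost. It means that the final test keeps its type I error when the rule is ignored. When the rule is followed, the power loss still occurs.

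A stated power for a primary hypothesis should therefore say whether the planned look is included. If the margin above 90% is small, following the plan's own guidance could take the cohort below the stated figure without either document saying so. Whoever applies the guidance also sees a 14% chance of success with no method attached, and so cannot tell what response rate, or what averaging over response rates, lies behind it.

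**Working it through.** **Inputs.** Null ORR 15% (SAP 7.1); 1-sided level 0.025 (SAP 3.2); exact binomial test (SAP 7.2.1). Cohort B: N = 90, alternative 30% (SAP 3.3), interim n = 35, stop at 6 or fewer (SAP 9). Cohort A: N = 60, alternative 35%, interim n = 25, stop at 4 or fewer.

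**Step 1: reproduce the stated power, no look.** The critical count r is the smallest with P(X ≥ r | N, 0.15) ≤ 0.025.
- Cohort B: P(X ≥ 20 | 90, 0.15) = 0.0434 and P(X ≥ 21 | 90, 0.15) = 0.0240, so r = 21. Power = P(X ≥ 21 | 90, 0.30) = 0.9355.
- Cohort A: P(X ≥ 15 | 60, 0.15) = 0.0291 and P(X ≥ 16 | 60, 0.15) = 0.0136, so r = 16. Power = P(X ≥ 16 | 60, 0.35) = 0.9344.

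The stated floor of 90% reproduces for both cohorts.

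**Step 2: power with the guidance followed.** With interim limit f, interim size n1 and true rate p:

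Power = Σ over x = f+1, …, n1 of P(X1 = x | n1, p) × P(X2 ≥ r − x | N − n1, p)

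This equals the no-look power minus the probability of meeting the limit and then succeeding had the cohort continued.
- Cohort B: P(X1 ≤ 6 | 35, 0.30) = 0.0650. Given that, the chance of eventual success at 30% is 0.651. Lost power = 0.0650 × 0.651 = 0.0423. Power = 0.9355 − 0.0423 = 0.8932.
- Cohort A: P(X1 ≤ 4 | 25, 0.35) = 0.0320, chance of eventual success 0.546. Lost power = 0.0320 × 0.546 = 0.0175. Power = 0.9344 − 0.0175 = 0.9169.

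| Cohort | No look | Guidance followed | Loss (points) |
|---|---|---|---|
| A (ORR 35%) | 93.4% | 91.7% | 1.7 |
| B (ORR 30%) | 93.5% | 89.3% | 4.2 |

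**Step 3: sensitivity to the approximate interim size.** Cohort B, limit 6, N = 90:

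| Interim n | Power |
|---|---|
| 34 | 88.2% |
| 35 | 89.3% |
| 36 | 90.2% |
| 37 | 90.9% |

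**Step 4: what the 14% could be.** With 6 responders in 35, success needs 15 or more in the remaining 55.
- Conditional probability P(X2 ≥ 15 | 55, p): 1.3% at p = 15%, 4.0% at the observed 6/35 = 17.1%, 71.7% at p = 30%. None matches 14%.
- Beta-binomial predictive probability, with priors that are assumed because the documents give none: 12.8% with Beta(0.15, 0.85), 13.9% with Beta(0.3, 0.7), 15.5% with Beta(0.5, 0.5), 17.9% with Beta(1, 1).
- The same approach for Cohort A at 4 of 25 gives 5.2% to 8.5%, in line with the stated figure of below 10%.

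**The case against.** The strongest reply is that nothing stated is wrong. The 90% claim is attached to N = 90 and the exact test, and for that test it is true with room to spare. Leaving a nonbinding futility rule out of the power statement is a common convention. Stopping is discretionary, so 89.3% is the lower end of a range whose upper end is 93.5%. The shortfall is 0.7 points, and one more evaluable participant at the look removes it.

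Most of that stands. A reader might infer that the sample size arithmetic is wrong, or that the design cannot deliver its stated power. The documents support neither reading: the figure reproduces, and the rule need not be followed. What remains is that the plan includes a look, the power sections are silent on it, and following the plan's own guidance costs about 4 points.

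A reader might also infer that the two cohorts breach a common standard, because one limit is accompanied by a figure below 10% and the other by 14%. Neither document sets 10% as a criterion. Each figure is reported as the consequence of a chosen count, and the cohorts differ in alternative, interim size and total size. The observed rates at the limits are close (4/25 = 16.0%, 6/35 = 17.1%).

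Nor does the point show that the Cohort B limit should become 5 of 35. That would raise power with the guidance followed to 92.0%, but it would cut the chance of stopping at a true ORR of 15% from 73% to 57%. It is a trade-off for the sponsor, not a correction.

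Finally, the 14% cannot be said to be a predictive probability. A conditional probability at an assumed ORR a little above 20% also gives about 14% (12.1% at 20%, 21.4% at 22%), although the documents state no such rate. The method is simply not named.

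**Conclusion.** The concern holds as a gap in reporting. The Cohort B floor of 90% is correct for the single-look exact test (93.5%) and does not account for the planned futility look. With the guidance always followed, power at an ORR of 30% is 89.3%, a loss of 4.2 points. Whether that lies below 90% turns on an interim size given only approximately, so the loss is the firmer finding. Cohort A loses 1.7 points and stays above 90%.

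These figures assume exactly 35 and 25 evaluable participants at the looks, final sizes of 90 and 60, the interim participants counted within the final total, and response status unchanged between the look and the final analysis. They describe each cohort's own test. Cohort B is tested only if Cohort A is significant, so the chance of a formal claim in Cohort B is lower still. Type I error is not at issue: 0.0240 for Cohort B without the look, and 0.0202 if the guidance is followed.

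The missing method behind the 14% and the figure below 10% is a secondary point of clarity. Both are consistent with a predictive probability under weak priors, but those priors are assumptions made here.

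**What to change.** In Protocol 10.1 and SAP 3.3, state power both ways, without the look and with the futility guidance followed: about 94% and 89% for Cohort B, about 93% and 92% for Cohort A. Drop the 90% floor for Cohort B or qualify it as applying to the test without the look. Add that the second figure assumes the look takes place at 35 participants, with 88.2% at 34 and 90.2% at 36.

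In Protocol 10.5 and SAP 9, name the method behind the two stated probabilities and, if a prior or an assumed ORR was used, give it.

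The cost is a few sentences and one slightly less favourable figure. Sample sizes, futility limits and the final test all stay as they are.

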10. CHANGES AND MODIFICATIONS TO THE ANALYSIS PLAN

All versions of the SAP are listed in [Table 7](#).

Table 7: Statistical Analysis Plan Versions

SAP Version	Date
Original	23 SEP 2020

10.1. Changes to Protocol-Defined Analyses

Not applicable.

10.2. Changes to the Statistical Analysis Plan

Not applicable.

APPENDIX A. PLANNED TABLES, FIGURES, AND LISTINGS

This appendix provides a list of the planned tables, figures and listings for the clinical study report. Shells are provided in a separate document for tables that are not in the Standard Safety Tables.

The lists of tables, figures, and listings are to be used as guidelines. Modifications of the lists that do not otherwise affect the nature of the analysis will not warrant an amendment to the SAP.

Tables

Table No.	Title	Population
Baseline and Demographic Characteristics		
1.1 Disposition		
1.1.1	Analysis Populations	All Enrolled
1.1.2	Summary of Participant Disposition	Safety
1.1.3	Summary of Number of Participants Enrolled by Country and Site	Safety
1.1.4	Summary of Protocol Deviations	Safety
1.2 Demography and Baseline Characteristics		
1.2.1	Summary of Demographics and Baseline Characteristics	Safety
1.3 Baseline Disease Characteristics		
1.3.1.1	Summary of Baseline Disease Characteristics	Safety
1.3.1.2	Summary of Baseline Disease Characteristics – Glioblastoma	Safety
1.3.2	Summary of Prior Systematic Cancer Therapy by WHO Drug Class and Preferred Term	Safety
1.3.3	Summary of Prior Cancer Therapy	Safety
1.4 Prior Medication and Concomitant Medication		
1.4.1	Summary of Prior Medications	Safety
1.4.2	Summary of Concomitant Medications	Safety
1.5 General Medical History		
1.5.1	Summary of General Medical History	Safety
Efficacy		
2.1 Primary Efficacy		
2.1.1	Summary of Best Response and Objective Response Rate – Cohort A and B	Efficacy
2.1.2	Summary of Best Response and Objective Response Rate – Cohort A and B	Per Protocol
2.2 Secondary Efficacy		
2.2.1	Summary of Progression-Free Survival – Cohort A and B	Efficacy
2.2.2	Summary of Duration of Response – Cohort A and B	Efficacy
2.2.3	Summary of Overall Survival – Cohort A and B	Efficacy
2.2.4	Summary of Best Change in Target Lesion Size	Efficacy

Table No.	Title	Population
Safety		
3.1 Dose Exposure		
3.1.1	Summary of Exposure and Duration of Exposure to Pemigatinib	Safety
3.1.3	Summary of Study Drug Compliance	Safety
3.2 Adverse Events		
3.2.1	Overall Summary of Treatment-Emergent Adverse Events	Safety
3.2.2	Summary of Treatment-Emergent Adverse Events by MedDRA System Organ Class and Preferred Term	Safety
3.2.3	Summary of Treatment-Emergent Adverse Events by MedDRA Preferred Term in Decreasing Order of Frequency	Safety
3.2.4	Summary of Treatment-Emergent Adverse Events by MedDRA System Organ Class, Preferred Term, and Maximum Severity	Safety
3.2.5	Summary of Treatment-Emergent Adverse Events by MedDRA System Organ Class, Preferred Term, and CTCAE Grade Category	Safety
3.2.6	Summary of Grade 3 or Higher Treatment-Emergent Adverse Events by MedDRA System Organ Class and Preferred Term	Safety
3.2.7	Summary of Grade 3 or Higher Treatment-Emergent Adverse Events by MedDRA Preferred Term in Decreasing Order of Frequency	Safety
3.2.8	Summary of Serious Treatment-Emergent Adverse Events by MedDRA System Organ Class and Preferred Term	Safety
3.2.9	Summary of Serious Treatment-Emergent Adverse Events by MedDRA Preferred Term in Decreasing Order of Frequency	Safety
3.2.10	Summary of Pemigatinib Treatment-Related Treatment-Emergent Adverse Events by MedDRA System Organ Class and Preferred Term	Safety
3.2.11	Summary of Pemigatinib Treatment-Related Treatment-Emergent Adverse Events by MedDRA Preferred Term in Decreasing Order of Frequency	Safety
3.2.12	Summary of Grade 3 or Higher Pemigatinib Treatment-Related Treatment-Emergent Adverse Events by MedDRA System Organ Class and Preferred Term	Safety
3.2.13	Summary of Pemigatinib Treatment-Related Serious Treatment-Emergent Adverse Events by MedDRA System Organ Class and Preferred Term	Safety
3.2.14	Summary of Treatment-Emergent Adverse Events With a Fatal Outcome by MedDRA System Organ Class and Preferred Term	Safety
3.2.15	Summary of Treatment-Emergent Adverse Events Leading to Pemigatinib Dose Reduction by MedDRA System Organ Class and Preferred Term	Safety
3.2.16	Summary of Treatment-Emergent Adverse Events Leading to Pemigatinib Dose Interruption by MedDRA System Organ Class and Preferred Term	Safety
3.2.17	Summary of Treatment-Emergent Adverse Events Leading to Discontinuation of Pemigatinib by MedDRA System Organ Class and Preferred Term	Safety
3.2.18	Summary of Sponsor-Defined Clinically Notable TEAEs by Category and Preferred Term	Safety
3.2.19	Summary of Grade 3 or Higher Sponsor-Defined Clinically Notable TEAEs by Category and Preferred Term	Safety
3.2.20	Summary of Serious Sponsor-Defined Clinically Notable TEAEs by Category and Preferred Term	Safety
3.2.21	Summary of Sponsor-Defined Clinically Notable TEAEs Leading to Pemigatinib Dose Reduction by Category and Preferred Term	Safety

Table No.	Title	Population
3.2.22	Summary of Sponsor-Defined Clinically Notable TEAEs Leading to Pemigatinib Dose Interruption by Category and Preferred Term	Safety
3.2.23	Summary of Sponsor-Defined Clinically Notable TEAEs Leading to Discontinuation of Pemigatinib by Category and Preferred Term	Safety
